Sample Size Considerations	
Because PKAN is an ultra-rare disease, we are limited to 64 participants for the Primary Cohort (15 in each arm + 4 potential dropouts allowing for 5% loss to follow-up) whom we will recruit from our established research registry, (prioritizing those participating in our “PKANready” ongoing natural history study) as well as by methods described within the protocol. When our double-blind enrollment goal is met, enrollment of up to 86 additional participants will shift to an open-label arm, designated the Open-label Cohort. Our primary objective is to estimate effects of the study product and we will prioritize effect sizes over statistical power in interpreting results. Still, we wish to include sufficient numbers to estimate effects in our secondary and exploratory analyses of CoASY mRNA expression levels with some precision. In preliminary cross-sectional data, we found that the mean CoASY delta Ct (dCt) measures were 1.4 standard deviations higher in classic PKAN children (n=8) than age-matched healthy controls (n=6) on the log₂ scale, where higher dCt indicates lower CoASY activity (mean=17.39 vs 16.85, SD=0.39). We anticipate that participants at all three dose levels will resemble healthy controls after 3±2 days, while the placebo group will show no change. We simulated this change from baseline for 12 participants per group. For the standard deviation, we performed one set of simulations using the upper limit of the 60% CI for the standard deviation (0.34-0.48) as a conservative estimate. We regressed the dCt value on four indicator variables for study arm after treatment, with the intercept representing the common mean baseline value, and included a random intercept to induce correlation between paired measurements. We then used a Wald test for $\beta_{\text{placebo}1} - (\beta_{\text{low}1} + \beta_{\text{mid}1} + \beta_{\text{high}1})/3 = 0$ at $\alpha=0.05$. Pooling over 1000 simulated datasets, we find that we reject the null in 85-95% of simulations, approximating power to detect this difference at one month between the active and placebo groups.

-----------------------------------	---

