For modeling and inferential tests, we will consider a p-value less than 0.1 to be significant if the magnitude and precision of the estimated effect support that conclusion. Covariates will be specified in the description below. We will perform extensive exploratory data analysis and checks of model fit and will transform variables with obvious departures from normality.

Analysis of primary endpoints

Safety Analysis

Comparisons of participants experiencing treatment-emergent adverse events and clinically-significant abnormalities on clinical labs will be reviewed for clinical significance in the Safety Analysis dataset, which includes all participants who consume at least one dose of the study product. Events expected as part of the usual disease course in PKAN, whether present at trial enrollment or not, will not be considered or captured as adverse events.

Frequencies of participants experiencing at least one adverse event (AE) will be displayed by body system and preferred term according to *Medical Dictionary for Regulatory Activities* (MedDRA) terminology. Detailed information collected for each AE will include a description of the event; duration; whether the AE meets criteria as a Serious Adverse Event (SAE); severity / grade of the event; relationship to study product; changes made to the study product in response to the AE /SAE; and clinical outcome. Severity of the AEs will be graded according to the NCI *Common Terminology Criteria for Adverse Events*, Version 4.0. If the event meets criteria as an SAE, the nature of the SAE will be classified using standard FDA criteria.

The number and percentage of patients who experienced any serious AE (SAE), treatment-emergent AE, and treatment-emergent SAE will be summarized, as well as the total number of events per arm. AE data will be presented for months 0-6 and 7-37 and cumulatively, as appropriate. Emphasis in the analyses will be placed on AEs classified as treatment-emergent.

Clinically-significant abnormalities on clinical labs will be tabulated similarly to AEs. The number and percentage of patients experiencing clinically-significant abnormalities will be compiled in summary tables to examine the distribution by collection month [0-1-3-6-7-9-12-18-24 (25) months for the Primary Cohort; and 0-1-3-6-12-18 (19) months for the Open-label Cohort].

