To estimate the **change in expression levels after 3±2 days of treatment compared to placebo**, we will use a mixed effects regression model of the form $CoASY_{ijt} = \beta_0 + \beta_{jt}I(group = j)I(time = t \text{ and } t > 0) + \alpha I(cPKAN) + b_i$, $j = \text{placebo, low, mid, high}$; $t = 1$. Each individual contributes two observations (baseline and after); b_i represents the random intercept for subject. Baseline, represented by β_0 , is constrained to be the same for all groups because of randomization. Our primary approach will treat time as binary (0=baseline, 1=treated), though this can later be expanded to capture differences between days 1-5 of treatment and include more time points. The β_{jt} represent mean changes from baseline for the three dose groups and placebo. An indicator for PKAN type (cPKAN or aPKAN) is included to reflect its role in stratified randomization. We will review regression coefficients as estimates of the magnitude of effect and $\beta_{\text{placebo}1} - (\beta_{\text{low}1} + \beta_{\text{mid}1} + \beta_{\text{high}1})/3 = 0$ with a two-sided alpha of 0.1 to determine whether CoASY mRNA expression levels rose in all the study product-treated participants after initiation of treatment compared to placebo.

Similarly, we will check for **treatment response when the placebo group initiates treatment after month 6** by recoding their observations to use months 6 as 0

(baseline). We will use the same regression model but expect $\beta_{\text{placebo}1}$ to differ from zero. Further, because PKAN types may differ in response, we will test for an **interaction effect between PKAN type and treatment** averaged over dose levels as $CoASY_{ijt} = \beta_0 + \beta_1 I(\text{aPKAN type}) + \beta_2 I(\text{time} = \text{post}) + \beta_{12} I(\text{aPKAN})I(\text{post}) + b_i$, where indicator variables represent active vs placebo, aPKAN vs classic, and β_{12} is the coefficient for their interaction. 50% of participants are expected to have aPKAN.

At six months, we expect CoASY mRNA expression levels to have decreased somewhat, and that **the group with the highest dose will show the lowest expression**. In addition to repeating the comparisons outlined for initiation of treatment above, we will test $\beta_{\text{low}1} > \beta_{\text{mid}1} > \beta_{\text{high}1} > \beta_{\text{placebo}1}$.

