- b. There will be **no difference in CoASY mRNA expression between 4'-PPT dose groups after 1 month of treatment**. Statistical tests will fail to reject the null and the magnitude of the difference will be small compared to the one-month change.
- c. **After 6 months of treatment, CoASY mRNA expression levels will vary inversely with 4'-PPT dose**, and
- d. There will be **no difference between initial dose groups [placebo/active] after up to 18 months on the same active dose**, consistent with down-regulation of CoASY activity in the presence of excess substrate, (i.e. feedback inhibition).

6. Study Product

The study product is 4'-phosphopantetheine (4'-PPT) formulated in a fruit-flavored syrup suitable for administration by mouth or via G-tube. Several factors contribute to the prediction that 4'-PPT is of very low toxic potential^[9]. First, it is a synthetic version of a naturally-occurring product of intermediary metabolism in the vitamin B5 pathway [See Figure 1]. Second, the compound has shown no evidence of toxicity when given to mice in doses far in excess of those used in this trial. Third and perhaps most important, it will be used in very low doses intended to mimic physiologic levels: all doses employed in the study are based on a range tested in the mouse model as the ‘minimum effective’, rather than the more usual ‘maximum tolerated’ doses. Although derived from mouse studies, the dose range to be used in this trial turns out to be remarkably close to the molar equivalent of the Recommended Daily Allowance (RDA) of pantothenate, the upstream vitamin the study product aims to replace, which itself shows little toxicity even in doses far in excess of the RDA, with no upper limit established by the Institute of Medicine^[10].

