Because PKAN is an ultra-rare disease, we are limited to 64 participants (15 in each arm + 4 potential dropouts allowing for 5% loss to follow-up) whom we will recruit from our established research registry, (prioritizing those participating in our "PKANready" ongoing natural history study) as well as by methods described within the protocol. This will be designated the "Primary Cohort". When our double-blind enrollment goal is met, enrollment of up to 86 additional participants will shift to an open-label arm; this will be designated the "Open-label Cohort". Enrollment into this cohort will be rolling, and thus the duration of follow up will vary based on the point of entry in the overall life of the

study. Our primary objective is to estimate effects of the study product and we will prioritize effect sizes over statistical power in interpreting results. Still, we wish to include sufficient numbers to estimate effects in our secondary and exploratory analyses of CoASY mRNA expression levels with some precision. In preliminary cross-sectional data, we found that the mean CoASY delta Ct (dCt) measures were 1.4 standard deviations higher in classic PKAN children (n=8) than age-matched healthy controls (n=6) on the \log_2 scale, where higher dCt indicates lower CoASY activity (mean=17.39 vs 16.85, SD=0.39). We anticipate that participants at all three dose levels will resemble healthy controls after 3 ± 2 days, while the placebo group will show no change. We simulated this change from baseline for 12 participants per group. For the standard deviation, we performed one set of simulations using the upper limit of the 60% CI for the standard deviation (0.34-0.48) as a conservative estimate. We regressed the dCt value on four indicator variables for study arm after treatment, with the intercept representing the common mean baseline value, and included a random intercept to induce correlation between paired measurements. We then used a Wald test for $\beta_{\text{placebo1}} - (\beta_{\text{low1}} + \beta_{\text{mid1}} + \beta_{\text{high1}})/3 = 0$ at $\alpha=0.05$. Pooling over 1000 simulated datasets, we find that we reject the null in 85-95% of simulations, approximating power to detect this difference at one month between the active and placebo groups.

b. Statistical plan for primary and secondary aims

Safety Analysis

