We will compare the number of participants retained in each arm at each of the follow-up time points [0-(0+1week)-1-3-6-(6M+1week)-7-9-12-18-24-25 months for the Primary Cohort; and 0-(0+1week) -1-3-6-9-12-18-19 for the Open-label Cohort], taking into account whether dropout seems plausibly related to study participation and the mean percent of study product consumed. High retention in the study and product consumption per-protocol will be considered evidence of tolerability.

Analysis of secondary endpoints

We will estimate a CoASY pharmacodynamic profile in response to different doses of the study product in the Per-Protocol dataset. CoASY mRNA expression levels are continuous, measured in normalized differences in cycle times (ΔCt) on the \log_2 scale. Lower ΔCt indicates higher expression levels. We will use regression models controlling for PKAN type to estimate mean levels by treatment arms, including mixed effects when modeling over multiple time points.

To estimate the **change in expression levels after 3±2 days of treatment compared to placebo**, we will use a mixed effects regression model of the form $CoASY_{ijt} = \beta_0 + \beta_{jt}I(group = j)I(time = t \text{ and } t > 0) + \alpha I(cPKAN) + b_i$, $j = \text{placebo, low, mid, high}$; $t = 1$. Each individual contributes two observations (baseline and after); b_i represents the random intercept for subject. Baseline, represented by β_0 , is constrained to be the same for all groups because of randomization. Our primary approach will treat time as binary (0=baseline, 1=treated), though this can later be expanded to capture differences between days 1-5 of treatment. The β_{jt} represent mean changes from baseline for the three dose groups and placebo. An indicator for PKAN type (cPKAN or aPKAN) is included to reflect its role in stratified randomization. We will review regression coefficients as estimates of the magnitude of effect and test $\beta_{\text{placebo}1} - (\beta_{\text{low}1} + \beta_{\text{mid}1} + \beta_{\text{high}1})/3 = 0$ with a two-sided alpha of 0.1 to determine whether CoASY mRNA expression levels rose in all the study product-treated participants after initiation of treatment compared to placebo.

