Subjects will be instructed to return all unused study product to the site at the end of each study time period, with pre-paid mailers provided along with blood draw supplies and the next time period's study product supply. Adherence to the study product regimen will be assessed by calculating actual product consumed / expected product consumption. In the event that the unused portion is lost, the study team will ask the participant to approximate. We will compare means and standard deviations among the four study arms during the first six months and among the three dose groups in the Primary Cohort in months 7-36.

Retention will be tabulated as the number participating at the end of each month from baseline to month 37 (including the final follow up visit), grouped by study arm and annotated with reason(s) for study exit. Exit may occur if the participant is lost to follow up or indicates that s/he is no longer willing or able to participate.

Baseline descriptive statistics

Intervention groups (4 groups of 15 participants each) and the direct to open-enrollment group will be compared on baseline characteristics, including PKAN type, age, gender, laboratory measurements, and CoASY mRNA expression levels using descriptive statistics. Inferential statistics will not be used.

Additional sub-group analyses

Age will be evaluated as a covariate in secondary analyses.

Tabulation of individual response data

Safety and tolerability events will be listed for individual participants by measure and time point. Individual CoASY expression profiles over time will be plotted for visual inspection.

e. Procedures to minimize bias

Measures to minimize bias

Randomization/masking procedures

Study statisticians will prepare randomization lists stratified by PKAN type and deliver these to the research pharmacy. The study team will remain blinded to treatment assignment throughout the study. The Independent Medical Monitor can instruct the Research Pharmacy to break the blind for a given subject if deemed medically necessary, or under conditions outlined in the DSMP. The research pharmacy will distribute the randomization scheme for data analysis purposes following standard procedures.

Evaluation of the success of blinding

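### The dose-averaged CoASY test supports a rise on average compared with placebo, not a rise in all treated participants; its alpha and time label also need reconciling

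*Combined protocol and SAP*

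**What the plan says.** Section 10.b (Analysis of secondary endpoints) fits a mixed model to baseline and one post-treatment value per participant, with a common baseline and a mean change for each of the four arms. It reviews the coefficients and tests whether the placebo change equals the average of the low, mid and high changes, "with a two-sided alpha of 0.1 to determine whether CoASY mRNA expression levels rose in all the study product-treated participants after initiation of treatment". The sentence ends by making the comparison one with placebo. The synopsis (Statistical Methods) gives the same purpose: "to determine whether CoASY mRNA expression levels rose in all the study product-treated participants after initiation of treatment".

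The power statement in Section 10.a and in the synopsis (Sample Size Considerations) concerns the same contrast but uses alpha 0.05. It describes the expected response at 3±2 days ("We anticipate that participants at all three dose levels will resemble healthy controls after" that interval) and simulates that change with 12 per group. It then reports that the simulations "reject the null in 85-95% of simulations, approximating power to detect this difference at one month between the active and placebo groups".

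Three other provisions bear on interpretation:
- The synopsis counts "a p-value less than 0.1 to be significant if the magnitude and precision of the estimated effect support that conclusion".
- The sample size text ranks effect sizes above power when results are interpreted.
- Section 10.d says "Individual CoASY expression profiles over time will be plotted for visual inspection".

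Section 5 adds hypothesis b, that the doses will not differ at one month ("Statistical tests will fail to reject the null and the magnitude of the difference will be small compared to the one-month change"), and hypothesis d, that the initial groups will not differ after up to 18 months on the same dose.

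**The concern.** The contrast has one degree of freedom and is built from arm means. It can be clearly non-zero when two doses respond and the third responds weakly or not at all. The sentence nevertheless makes it the means of deciding about all treated participants, and the hypotheses in the synopsis and in Sections 3 and 5 use the same word. The protocol itself expects slightly different time courses by dose, so a weaker response at one dose by day 3 is a realistic pattern.

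At stake is how the proof-of-concept result is reported. A rejected average could be written up as a uniform response. Similarly, hypotheses b and d could be declared supported because a small study failed to find a difference.

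Two inconsistencies affect the same test. Power is given for an alpha that the analysis does not use, and the power figure is labelled with a time point other than the one simulated.

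**Working it through.** **Inputs (Section 10.a unless stated).** Means 17.39 and 16.85, so the assumed effect is 0.54 dCt; SD 0.39, with 0.48 as the conservative value; 12 per arm simulated and 15 per arm planned; stated power 85-95% at two-sided 0.05; analysis alpha 0.10 (Section 10.b).

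**The plan's own figures.** 0.54/0.39 = 1.38, stated as 1.4. The 60% interval for the SD on 12 degrees of freedom is 0.340-0.484, stated as 0.34-0.48. Both reproduce. The power depends on a within-subject correlation that is not given:
- If 0.39 and 0.48 are residual SDs with an added random intercept and the correlation is 0.25, power is 96.0% and 85.5%, close to the stated range.
- If they are total SDs and the correlation is 0 to 0.5, power is 98.6-99.8% and 92.1-97.4%.

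The stated range is therefore attainable but cannot be verified. The rest is calibrated to the stated power.

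**Calibration.** Noncentrality L = 1.960 + z(power). At 12 per arm, L = 1.960 + 1.036 = 2.996 (85%) to 1.960 + 1.645 = 3.605 (95%). At 15 per arm, multiply by sqrt(15/12) = 1.118, giving 3.350 to 4.030.

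**Rejection at alpha 0.10.** The probability is Φ(fL − 1.645), where f is the average effect over the three doses as a fraction of the full effect.

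| Pattern | f | 12 per arm | 15 per arm |
|---|---|---|---|
| All doses fully active | 1 | 0.912-0.975 | 0.956-0.991 |
| One dose at half effect | (1+1+0.5)/3 = 5/6 | 0.803-0.913 | 0.874-0.957 |
| One dose inert | (1+1+0)/3 = 2/3 | 0.638-0.776 | 0.722-0.851 |

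Example (one inert dose, 12 per arm, lower end): Φ(2/3 × 2.996 − 1.645) = Φ(0.353) = 0.638.

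Simulation of the planned mixed model (4,000 trials per setting, SD set to give 85% or 95% power, correlation 0 or 0.5) agrees: 0.638-0.793 and 0.713-0.858 with one inert dose. If 0.39-0.48 are total SDs and the correlation is 0.3-0.5, the inert-dose figures are higher, at 75-93% (12 per arm) and 83-97% (15 per arm).

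**Alpha.** The first row also answers the alpha question. A power of 85-95% at 0.05 becomes 91.2-97.5% at 0.10 with 12 per arm.

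**Precision between doses.** The averaged contrast has variance proportional to 1 + 1/3 = 4/3, and a two-arm difference has variance proportional to 2. The ratio is 1.5, so the noncentrality for one full dose effect is L/sqrt(1.5). The 95% half-width, as a fraction of 0.54, is 1.96 × sqrt(1.5)/L. This gives 0.80-0.67 at 12 per arm (0.43-0.36 dCt) and 0.72-0.60 at 15 per arm (0.39-0.32 dCt). Failure to reject is therefore compatible with a dose difference more than half the size of the whole expected effect. Similar precision at later visits is an assumption.

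**Time labels side by side.** The synopsis hypotheses, Section 3 and the analysis text (synopsis and Section 10.b) say 3±2 days. The simulation paragraph also describes 3±2 days but labels its result one month. Section 5, hypothesis a, says one month.

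**The case against.** The strongest reply is that the sentence defines its own meaning. It specifies a pooled contrast and a comparison with placebo, and Section 10.a describes the result as active versus placebo groups. On that reading, which is the most natural one, the contrast is right and only the wording is loose. That stands.

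The plan also does not rest on the p-value alone. The coefficients are reviewed, significance is conditional on magnitude and precision, and effect sizes come first. Dose-specific analyses follow at six months and in the longitudinal model, and the blinded phase is declared not to be dose-finding. These steps would probably expose an inert dose. None of them, however, states what would justify the word all.

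Hypothesis b does not rely on non-rejection alone, since it also asks that the difference be small relative to the one-month change. That is a fair point, but no size is given.

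Testing at 0.10 after sizing at 0.05 is conservative. Because biomarker samples are scheduled at both day 3 and month 1, a one-month hypothesis is testable too. Both points stand; the labels still disagree.

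**Conclusion.** The point holds as one of wording, reporting and consistency. A rejected contrast supports a difference from placebo averaged over doses, and it is likely (64-85% across the two sample sizes) even with one inert dose. These figures rest on the plan's stated power being correct and on a normal approximation; the total-SD reading makes the inert-dose figures higher.

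Three stronger readings are not supported:
- A reader might infer that the plan claims a rise in every individual. The comparison with placebo makes that unlikely, and no test of means could address it.
- A reader might infer that the alpha mismatch undermines the sample size. It works the other way: the stated power is conservative for the test actually planned.
- A reader might infer that the power was simulated at a different visit from the test. The paragraph describes the 3±2-day change, so this is a contradictory label.

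The endpoint is secondary and proof-of-concept, and the primary safety objective is unaffected.

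**What to change.** 1. In Section 10.b and the synopsis, state the conclusion of the averaged test as a rise on average across doses compared with placebo.
2. From the same model, report each dose-versus-placebo estimate and the dose-to-dose differences with confidence intervals. For hypotheses b and d, interpret those intervals and do not treat non-rejection as evidence of equality.
3. State power for the alpha actually used. Taking the plan's range as given, that is about 91-97.5% at 0.10 with 12 per arm.
4. Correct the one-month label on the power figure in Section 10.a and the synopsis to 3±2 days, and reconcile Section 5, hypothesis a, with the synopsis hypotheses, Section 3 and the analysis text.

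This costs some rewording and a few extra contrasts from the planned model. It needs no new data and takes no power from the averaged test; the dose-to-dose intervals will be wide.

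A rule requiring every dose to beat placebo is not needed. If the sponsor wanted one, its power would have to be worked out first, because it depends on the unstated SD and correlation reading. At alpha 0.10 with 12 per arm it is about 59-79% when calibrated to the plan's power, against about 71-99.8% if 0.39-0.48 is the total SD (correlation 0-0.7).

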Similarly, we will check for **treatment response when the placebo group initiates treatment after month 6** by recoding their observations to use month 6 as 0 (baseline). We will use the same regression model but expect $\beta_{\text{placebo}1}$ to differ from zero. Further, because PKAN types may differ in response, we will test for an **interaction effect between PKAN type and treatment** averaged over dose levels as $CoASY_{ijt} = \beta_0 + \beta_1 I(aPKAN \text{ type}) + \beta_2 I(time = post) + \beta_{12} I(aPKAN)I(post) + b_i$, where indicator variables represent active vs placebo, atypical PKAN vs classic, and β_{12} is the coefficient for their interaction. 50% of participants are expected to have aPKAN.

At six months, we expect CoASY mRNA expression levels to have decreased somewhat, and that the group with the highest dose will show the lowest expression. In addition to repeating the comparisons outlined for initiation of treatment above, we will test $\beta_{\text{low}1} > \beta_{\text{mid}1} > \beta_{\text{high}1} > \beta_{\text{placebo}1}$.

As a final step, we will develop a longitudinal model to characterize CoASY mRNA expression profiles over the entire 24-month study period. We plan to use a mixed effects model with random intercept and slope to account for correlation between measurements and to allow individuals to vary from the group mean. We will explore a number of possible parameterizations of the time effect, including fractional polynomials and splines. We will allow for different trajectories by (a) dose group and (b) PKAN type in separate models with a group x time interaction. This model will take the general form $CoASY_{ij} = \beta_0 + \beta_1 t_{ij} + \beta'_2 group + \beta_3 t_{ij} \times group + b_{1i} + b_{2i} t_{ij}$, where t_{ij} represents time on treatment in months (including partial months as decimals) and group indicates dose group or PKAN type, depending on the model.

c. Statistical plan for exploratory aim

Sample Size and Statistical Power Issues

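### The Month 6 crossover check reuses a common-baseline model whose stated justification, randomization, no longer applies once only the placebo arm is re-based

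*Combined protocol and SAP*

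**What the plan says.** Section 10.b (Analysis of secondary endpoints) sets out a mixed model for the first days of treatment. It has one intercept, a post-baseline coefficient for each of the four arms, an indicator for PKAN type and a random intercept per person. Baseline "is constrained to be the same for all groups because of randomization". The initial contrast is tested "with a two-sided alpha of 0.1", and the synopsis applies a 0.1 threshold to inferential tests generally.

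The next paragraph turns to the placebo arm's start on active product. It re-bases the placebo participants "by recoding their observations to use month 6 as 0 (baseline" and continues: "We will use the same regression model but expect" the placebo coefficient to be non-zero. The synopsis (Statistical Methods) describes the same procedure. Neither place gives the re-based arm its own intercept, restricts the fit to that arm, or adds a term for calendar time.

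The schedule of activities for the Primary Cohort places the first biomarker draw at Screening and further draws at Month 6 and at Month 6 + 3 days.

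**The concern.** Randomization makes the four arm means equal in expectation before treatment. After the recoding, the active arms still supply their pre-treatment values as time zero while the placebo arm supplies Month 6 values. These two baselines lie six to eight months apart, because the first draw is at Screening, which may fall up to two months before Month 0. Nothing in the design makes them equal.

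The planning assumption that placebo does not change is tied to the first 3 ± 2 days. It says nothing about six months. Participants who miss too many visits in the double-blind phase are terminated, and the biomarker analysis uses the Per-Protocol set, so those still contributing at Month 6 may also be a selected group.

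If the placebo mean has moved by Month 6, the shared intercept pulls that arm's baseline back towards the active arms' starting level. Part of the earlier movement is then reported as change after starting 4'-PPT. Lower dCt means higher expression, so a downward drift inflates the expected response and an upward drift attenuates it.

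**Working it through.** **Inputs from the documents.** Four equal arms of 15; two observations per person; effect and SD from "mean=17.39 vs 16.85, SD=0.39", a difference of 17.39 − 16.85 = 0.54 dCt; two-sided alpha 0.10.

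**Inputs not in the documents, so assumed.** The within-person correlation ρ, taken from 0.3 to 0.9, and the placebo drift d between the first baseline and Month 6, taken as 0 or 0.20 dCt (0.20/0.54 = 37% of the planned effect). SD 0.39 is treated as the total SD at both visits.

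**The plan's own figure.** There is none for the crossover check. The stated power of 85–95% is for the initial placebo-versus-active contrast: "We simulated this change from baseline for 12 participants per group", alpha 0.05. Its inputs reproduce: 0.54/0.39 = 1.38 (stated as 1.4), and the 60% interval for the SD on 12 degrees of freedom is 0.340–0.484. The power itself depends on an unstated correlation. Taking 0.39 and 0.48 as residual SDs, with a random-intercept SD 0.6 times as large (ρ about 0.26), gives about 96% and 85%. That figure is not in dispute.

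**Bias.** Let ȳ_j0 and ȳ_j1 be the arm means at time zero and after, and ȳ_00 the mean of the four time-zero means. With stratified, balanced arms the PKAN-type term drops out, and generalized least squares gives

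β̂_j1 = (ȳ_j1 − ȳ_00) − ρ(ȳ_j0 − ȳ_00).

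Shift both placebo means by d. Then ȳ_00 moves by d/4, and the placebo coefficient moves by (d − d/4) − ρ(d − d/4) = 0.75(1 − ρ)d. Each active coefficient moves by −0.25(1 − ρ)d, so a placebo-minus-active contrast would move by (1 − ρ)d.

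**Standard error.** Var(β̂_placebo1) = (σ²/n)[(1 − ρ²) + (1 − ρ)²/4], with σ²/n = 0.1521/15 = 0.01014. For the paired change in the placebo arm alone the variance is (σ²/n) × 2(1 − ρ).

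**False positives with no true response, d = 0.20**, by normal approximation, P(|Z + bias/SE| > 1.645):

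| ρ | bias | SE, common intercept | bias/SE | rejection at nominal 10% | SE, paired |
|---|---|---|---|---|---|
| 0.3 | 0.105 | 0.102 | 1.03 | 27% | 0.119 |
| 0.5 | 0.075 | 0.091 | 0.83 | 21% | 0.101 |
| 0.7 | 0.045 | 0.073 | 0.61 | 16% | 0.078 |
| 0.9 | 0.015 | 0.044 | 0.34 | 12% | 0.045 |

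With d = 0 the bias is zero and the rate is nominal. REML fits to simulated data with d = 0.20 gave mean placebo coefficients of 0.105, 0.074 and 0.029 and rejection rates of 28%, 23% and 15% at ρ = 0.3, 0.5 and 0.8. With a separate intercept for the re-based arm, the bias stayed within about ±0.006 and rejection was 9–12%.

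**Effect on a real response of 0.54.** At ρ = 0.3 an adverse drift of 0.20 leaves 0.54 − 0.105 = 0.435. Dividing by 0.102 gives 4.25, or power above 99%. A drift of a full SD (0.39) leaves 0.54 − 0.205 = 0.335, a ratio of 3.27 and power of about 95%. For d = 0.20 the estimate is distorted by 3% to 19% of 0.54 (0.015/0.54 to 0.105/0.54).

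**The case against.** The strongest reply is that the text does not say who enters the crossover fit. It recodes the placebo observations and names one coefficient. If the model were fitted to the placebo arm alone, the intercept would be that arm's own Month 6 mean and nothing would leak. This reading is possible but less literal: the plan reuses the same model, which has arm-specific coefficients and a cross-arm constraint, and mentions no restriction. Re-basing every arm to Month 6 would not help, since Section 5 expects Month 6 levels to differ by dose, which contradicts a common intercept.

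The second reply is that the drift is hypothetical. This stands. No passage gives a drift or says that CoASY expression moves untreated over six months. A drift of 0.39 would be 72% of the whole gap between patients and controls (0.39/0.54), and nothing in the documents supports a movement that large. A high correlation also shrinks the leak.

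Third, there are partial safeguards. A p-value below 0.1 counts only if magnitude and precision agree, model fit will be checked, individual profiles will be plotted, and the later longitudinal model carries a group term. These make a false signal easier to notice but do not correct the crossover estimate.

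A reader might infer that the flaw could hide a genuine crossover response, or that the check is offered as confirmation of the day-3 effect. The documents support neither. At the planned effect and SD 0.39, power stays at about 95% or more even with a 1-SD adverse drift. The plan presents this only as a check, and it is not among the listed secondary hypotheses.

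**Conclusion.** The concern holds for the analysis as literally written. The common baseline is carried into a comparison that its stated justification does not cover, and the estimated crossover response then absorbs 0.75 × (1 − ρ) of any placebo drift. At an assumed drift of 0.20 dCt, with 15 per arm and SD 0.39, the bias is 0.015–0.105 and the false-positive rate about 12–27% for ρ from 0.9 to 0.3. These sizes rest wholly on the assumed drift and correlation. The consequence is an inflated or attenuated estimate, or extra false positives if there is no response. The check supports a secondary, proof-of-concept biomarker; the primary safety and tolerability endpoints are untouched. It should be corrected because the remedy is simple and uses samples already scheduled.

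**What to change.** Replace the crossover sentence in Section 10.b and in the synopsis. Estimate the response within the former placebo arm alone, as the paired change from Month 6 to Month 6 + 3 days, adjusted for PKAN type. Alternatively, keep the four-arm model but give the re-based arm its own intercept. In either case, state that this is an uncontrolled pre/post estimate.

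The cost is one sentence and a small loss of precision: SE about 0.12 instead of 0.10 at ρ = 0.3, and 0.078 instead of 0.073 at ρ = 0.7. For a change of 0.54 with 15 participants and two-sided alpha 0.10, the paired analysis has 97.5% power at SD 0.39 and 90.0% at SD 0.48, both at the unfavourable ρ = 0, and more at any higher correlation. No additional visits or samples are needed.
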